2.4. Primary Outcomes

Incidence of hospitalization events (per patient-year)

- Length of hospitalization (hospital days per patient-year)
- Mortality
- 4-year survival

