3.1.2.2. Multivariate analysis

Considering that the results of analyses that include effect measures may be compromised by potential confounding bias given the non-experimental design of the study, it has been

proposed that statistical models incorporate propensity score analyses using inverse probability of treatment weighting (IPTW) methods. These analyses will have the following steps:

These analyses will have the following steps 1:

- 1. Data preparation: This stage includes the selection of covariates, and the assessment of data balance and the pattern of missing data. Not only the variables that are associated with the type of dialysis and with each of the outcomes used in this research will be selected, but also those that are associated only with the outcome, since it has been reported that this decision can increase the power to evaluate the treatment effect ². In the event that the handling of missing data is required, multiple imputation methods with chained equations will be carried out, carrying out the imputation separately in each exposure group ³.
- 2. Propensity score (PS) estimation: Given the dichotomous nature of the exposure, these scores will be estimated using logistic regression methods ⁴.
- 3. Application of the PS method: As mentioned before, the IPTW method will be applied, considering that it has advantages such as sample size optimization (it does not eliminate observations that cannot be matched) and versatility for its use with different multivariate analysis methods ⁵.

¹Austin PC, Stuart EA. (2015) Moving towards best practice when using inverse probability of treatment weighting (IPTW) using the propensity score to estimate causal treatment effects in observational studies. Stat Med 10;34(28):3661-79.

²Cuong, N. V. (2013). Which covariates should be controlled in propensity score matching? Evidence from a simulation study. Statistica Neerlandica, 67(2), 169–180.

³Puma, MJ, Olsen, R.B., Bell, S.H., & Price, C. (2009). What to do when data are missing in group randomized controlled trials. Washington, DC: National Center for Education Evaluation and Regional Assistance, Institute of Education Sciences, US Department of Education.

⁴Setoguchi, S., Schneeweiss, S., Brookhart, MA, Glynn, RJ, & Cook, E.F. (2008). Evaluating uses of data mining techniques in propensity score estimation: A simulation study. Pharmacoepidemiology and Drug Safety, 17(6), 546–555.

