⁵Austin PC, Stuart EA. (2017) The Performance of Inverse Probability of Treatment Weighting and Full Matching on the Propensity Score in the Presence of Model Misspecification When Estimating the Effect of Treatment on Survival Outcomes. Stat Methods Med Res, 26(4), 1654-1670

- 4. Evaluation of the balance of covariates: It will be carried out with graphical methods (QQ plots for continuous variables and bar graphs for nominal variables), and with descriptive numerical methods (standardized mean differences and variance ratios) and inferential methods (t tests and rank sum tests) ⁶.
- 5. Estimation of treatment effect: Treatment effects, according to the type of outcome, will be estimated using generalized linear models with weighting of the observations in the sample ⁷.
- 6. Sensitivity analysis: This analysis will be performed to determine the magnitude of the bias that may be produced by the omission of covariates. For this analysis, the methodology proposed by Carnegie, Harada, Dorie and Hill will be used ⁸.

In accordance with the specific objectives set out in the protocol, the following types of analysis are proposed:

- 1. For the objectives related to the comparison of time to hospitalization and time to death event between both cohorts, the respective incidence rates for each group and the survival functions will be calculated using Kaplan-Meier estimators.
 Comparisons between the survival functions of each of the two groups will be made with log- rank, Tarone-Ware or Peto-Peto Prentice tests, depending on the censoring pattern. Additionally, Cox models will be used to estimate the strength of association between type of treatment and time to event using the HRs metric.
 In these models, weighted samples will be used with the IPTW method and a group of time-dependent covariates will be incorporated (serum albumin, PEW, MIS, hs CRP, type of dialyzer).
- 2. To meet the objectives related to counting variables (days of hospitalization and non-fatal cardiovascular events), Poisson regression models or negative binomial

⁶Austin P.C. (2009) Balance diagnostics for comparing the distribution of baseline covariates between treatment groups in propensity-score matched samples. Stat Med 10;28(25):3083-107

⁷Austin P.C. (2016) Variance Estimation When Using Inverse Probability of Treatment Weighting (IPTW) With Survival Analysis. Stat Med. 35 (30), 5642-5655

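### IPTW is attached only to the Cox models: the Kaplan-Meier curves and rank tests for death and hospitalization are not stated to be weighted, which leaves 4-year survival without a confounding-adjusted estimate

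*SAP*

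**What the plan says.** SAP section 2.4 lists mortality and "4-year survival" among the primary outcomes. Section 3.1.2.2 opens by accepting that "results of analyses that include effect measures may be compromised by potential confounding bias given the non-experimental design of the study". For that reason it is "proposed that statistical models incorporate propensity score analyses using inverse probability of treatment weighting (IPTW) methods". Step 5 of that procedure says that treatment effects "will be estimated using generalized linear models with weighting of the observations in the sample".

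Item 1 of the analysis list in the same section covers time to hospitalization and time to death, in this order:

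- For each group, "the survival functions will be calculated using Kaplan-Meier estimators".
- The two curves are then compared; the comparisons "will be made with log- rank, Tarone-Ware or Peto-Peto Prentice tests, depending on the censoring pattern".
- Cox regression follows as an added analysis, to give a hazard ratio for dialyzer type.
- Weights enter only at this last stage: "In these models, weighted samples will be used with the IPTW method". The same Cox models also carry albumin, PEW, MIS, hs CRP and type of dialyzer as time-dependent terms.

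No sentence says that the curves or the rank tests are weighted, and none says that they are not. No criterion links a censoring pattern to a test. Nothing says whether the rank test or the Cox model settles the comparison.

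**The concern.** Section 3.1.2.1 states that treatment was not randomly assigned. A crude curve and a crude rank test then mix any dialyzer effect with differences in case mix, which is the problem the propensity score was brought in to address.

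The gap matters most for 4-year survival. This is a probability at a time point, and a hazard ratio does not supply it. The Cox model as specified also conditions on laboratory and nutritional values measured during follow-up, so its hazard ratio is not the adjusted counterpart of the curves. The two analyses can disagree, and the SAP does not say which one stands.

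A lesser matter is that the choice among three tests with different time weighting is left open until the censoring has been seen.

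**Working it through.** **Where weighting applies.** The SAP gives no figure for the survival comparison; its only power statement concerns the hospitalization rate ratio. The first check is therefore textual.

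- In item 1, the nearest antecedent of the phrase that introduces weighting is the Cox models.
- The opening of section 3.1.2.2 speaks of statistical models, and step 5 of generalized linear models. A Kaplan-Meier estimate and a rank test are neither.
- The G methods in item 4 take albumin, not dialyzer, as the exposure. They do not yield adjusted survival by dialyzer group.

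So no planned analysis is stated to give a confounding-adjusted 4-year survival by dialyzer.

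**Possible size of the bias (inputs assumed, since the SAP gives no baseline distributions).** Take one binary confounder with hazard ratio 2, prevalence p1 in the MCO group and p0 in the high-flux group, and no dialyzer effect. The ratio of average hazards at the start is

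crude HR = (2·p1 + 1 − p1) / (2·p0 + 1 − p0) = (1 + p1) / (1 + p0).

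| p1 | p0 | Crude HR | Imbalance reversed |
|---|---|---|---|
| 45% | 50% | 1.45/1.50 = 0.97 | 1.50/1.45 = 1.03 |
| 40% | 50% | 1.40/1.50 = 0.93 | 1.50/1.40 = 1.07 |
| 35% | 55% | 1.35/1.55 = 0.87 | 1.55/1.35 = 1.15 |

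**Effect on the crude test.** Simulation with 564 and 534 patients (SAP sample size section), no dialyzer effect and 2,000 replicates. Assumed: death hazard 0.09 per year without the confounder, exponential censoring at 0.15 per year, follow-up capped at 4 years. Rejection by the unweighted log-rank test at a two-sided 5% level:

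| Prevalence, high-flux vs MCO | HR 1.5 | HR 2.0 | HR 2.5 |
|---|---|---|---|
| 50% vs 45% | 6.2% | 5.3% | 6.8% |
| 50% vs 40% | 7.3% | 11.1% | 13.9% |

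The Monte Carlo standard error is about 0.5 points near 6% (√(0.06·0.94/2000) = 0.0053), so the first row is hard to tell from 5%.

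**Choice among three tests.** Null simulation with the same group sizes and 4,000 replicates. Assumed: death hazards of 0.08, 0.12 and 0.16 per year, censoring of 0.1 or 0.2 per year in both groups, or 0.1 vs 0.3.

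- Each test alone rejects in 4.3–5.4% of replicates.
- Always taking the most favourable of the three rejects in 5.1–6.3%.
- The three statistics correlate at 0.98 or more. Three independent tests would give 1 − 0.95³ = 14.3%.
- A separate set of 4,000 null cohorts gave 5.8% for mortality and 6.5% for hospitalization. Its event and censoring rates are not available, so 6.5% is best taken as a rough upper end.

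**The case against.** The SAP is silent here; it does not declare the curves crude. Item 1 sits in a section whose premise is weighting, step 5 adapts the effect estimate to the type of outcome, and the source cited there is, by its title, about variance estimation for weighted survival analysis. The authors may have intended weighting throughout. That stands as a caution about wording, but not as a specification: the one sentence in item 1 that assigns weights assigns them to the Cox models.

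A reader might infer that the headline p-value for mortality is confounded. The SAP does not support that. It names no analysis as decisive, and it assigns the strength of association to a weighted Cox hazard ratio, so an IPTW-weighted comparison of time to death is planned. What remains is that this hazard ratio does not deliver 4-year survival, carries covariates measured after baseline, and has no stated rank relative to the test.

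A reader might also infer that the test will be picked for its result. The stated trigger is the censoring pattern, which can be inspected without comparing outcomes. Taking the best of three is therefore a worst case and not the written procedure, and even then it adds little.

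Finally, the confounder's strength, imbalance and direction are all assumed. The figures show what a crude comparison can do, not what this one will do. At a 5-point imbalance the distortion is small.

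**Conclusion.** The point holds in this form: as written, the Kaplan-Meier curves and rank tests for time to death and time to hospitalization are not stated to be weighted. Carried out literally, they are crude comparisons of non-randomised groups, contrary to the SAP's own warning, and 4-year survival has no adjusted estimate.

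Under the assumed single confounder, a null effect could appear as a hazard ratio of 0.87 to 0.97, or 1.03 to 1.15 if the imbalance runs the other way. With a 10-point imbalance, the crude log-rank test would reject in about 7–14% of null studies. The open choice of test is secondary, at most about 5–6.5% against a nominal 5%.

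The reading of the text does not depend on these assumptions; only the sizes do. The plan should be changed before the analysis starts.

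**What to change.** In section 3.1.2.2, item 1:

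- Estimate survival with IPTW-weighted Kaplan-Meier curves, and report the weighted 4-year survival difference with a bootstrap confidence interval that re-estimates the propensity score in each resample.
- Prespecify one weighted test for both time to death and time to hospitalization, and state that it decides. One option is the robust Wald test from an IPTW Cox model containing dialyzer only, without time-dependent albumin, PEW, MIS and hs CRP, so that it matches the weighted curves. A Cox model with those covariates can stay as a separate, supporting analysis.
- Label the crude curves and a single crude log-rank test as descriptive, and delete the choice among three tests.

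The cost is SAP wording and slightly more analysis work, since the weights are already planned. Weighting may widen the intervals.

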The concept of offering greater removal of protein-bound uremic toxins and medium molecular weight molecules makes HD based on this type of medium cut-off membranes, generically called expanded hemodialysis (MCO), increase (expand) the clearance capacities of the membrane, constituting an important therapeutic step with which positive results have been obtained in some efficacy studies, aimed at evaluating inflammation, and the clearance of medium molecules (8).

Although current renal replacement therapy systems have reduced patient morbidity and mortality and significantly improved their quality of life, they have not achieved an efficiency equivalent to that of the kidney. New membranes for dialysis systems have recently been developed (medium cut -off membranes (COMs) that allow the filtration of medium molecular weight molecules and that, in some studies, have shown promising results. However, for this new technology, there is still little information from longitudinal studies with sufficient follow-up time on clinical outcomes of importance for the patient and health systems, such as survival, frequency of cardiovascular events or hospitalization.

This study aims to establish the role of serum albumin levels, as well as that of markers of inflammation and malnutrition on outcomes such as mortality, non-fatal cardiovascular

events, hospitalization and hospital days in patients on hemodialysis, treated with medium cut-off (MCO) or high flux (HD AF) membranes.

2. Objectives and outcomes

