2.2. Specific objectives

- 1. To describe the demographic and clinical characteristics of both cohorts (MCO and HD AF).
- 2. To estimate and compare the days of hospital stay and the incidence of mortality and hospitalization in the studied cohorts.
- 3. To compare the cumulative hospitalization time during participation in the study, between patients receiving MCO and those receiving HD AF.
- 4. To compare the time to death event between patients receiving MCO and those receiving HD AF.
- 5. To compare the frequency of non-fatal cardiovascular events in both cohorts.
- 6. To estimate the association between serum albumin levels and the outcomes mortality, non-fatal cardiovascular events, hospitalization events and days of hospital stay, controlling for the effect of third variables such as PEW, MIS, hs CRP, type of dialyzer.

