3.1.2.1. Bivariate analysis

1. Since there is no random assignment to treatments, these analyses will be performed to compare baseline characteristics between the two groups and to assess differences between variables with repeated measures, over time. The variables that will be incorporated into these analyses will be: Analysis are Albumin, PEW, MIS, hs CRP, dialyzer type. Longitudinal analysis of covariance will be used considering that in this approach the outcome variable, which is measured during different time periods, is adjusted by the baseline value.

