⁸Carnegie, N.B., Harada, M., Dorie, V., & Hill, J. (2016). treatSens: Sensitivity analysis for causal inference. Retrieved from https://cran.r-project.org/web/packages/treatSens/index.html

regression models will be used in case of overdispersion in the outcome variable. Within these models, the covariates that will be candidates for inclusion in the models are:

- a. For the outcome days of hospitalization: Serum albumin, PEW, MIS, hs CRP, dialyzer type
- 3. For non-fatal cardiovascular events outcome: Serum albumin, PEW, MIS, hs CRP, dialyzer type
- 4. For the objective related to the estimation of the association between serum albumin levels and the outcomes of mortality, non-fatal cardiovascular events, hospitalization events and days of hospital stay, the use of linear mixed models for longitudinal data is proposed. This strategy allows modeling the association between repeated measurements of independent variables and the proposed outcomes, in the presence of other variables that also vary over time. These models involve the combination of fixed effects and random effects models, and allow the inclusion of variables that change over time. To identify potential confounding variables, a directed acyclic causal diagram (DAG) will be performed. Additionally, G methods will be used for longitudinal data, which allow estimating the causal effect of an exposure that varies over time (in this case albumin levels) in the presence of confounding variables that also vary over time (hs CRP, MIS, PEW, FRR, type of dialyzer) that are in turn affected by the exposure. These methods may be more robust than traditional regression-based methods. The parametric G- formula and the weighted inverse probability of treatment estimation with marginal structural models 9will be used 10.11

⁹James M. Robins, Sander Greenland, Fu-Chang Hu. Estimation of the Causal Effect of a Time-Varying Exposure on the Marginal Mean of a Repeated Binary Outcome, J Am Stat Assoc. 1999; 94:447, 687-700.

¹⁰Miguel A Hernán, Babette Brumback, James M Robins. Marginal Structural Models to Estimate the Joint Causal Effect of Nonrandomized Treatments. J Am Stat Assoc. 2001; 96:454, 440-448.

¹¹Sally Picciotto, Miguel A. Hernán, John H. Page, Jessica G. Young, James M. Robins. Structural Nested Cumulative Failure Time Models to Estimate the Effects of Interventions. J Am Stat Assoc. 2012;107:499, 886-900.

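### The weighted Cox models for the MCO versus high-flux hazard ratio also condition on time-updated albumin, PEW, MIS and hs CRP, so the HR is not the total dialyzer effect if the membrane changes any of these markers

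*SAP*

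**What the plan says.** SAP section 3.1.2.2, analysis item 1, covers the comparison of time to hospitalization and time to death between the cohorts. "Cox models will be used to estimate the strength of association between type of treatment and time to event using the HRs metric". These models use the IPTW-weighted sample, and "a group of time-dependent covariates will be incorporated (serum albumin, PEW, MIS, hs CRP, type of dialyzer"). The wording is a commitment, not an option. The matching objective in section 2.2 is "To compare the time to death event between patients receiving MCO and those receiving HD AF".

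Analysis item 2, on Poisson or negative binomial models, is looser: "the covariates that will be candidates for inclusion in the models are", followed by "For the outcome days of hospitalization: Serum albumin, PEW, MIS, hs CRP, dialyzer type" and, for the other count outcome, "For non-fatal cardiovascular events outcome: Serum albumin, PEW, MIS, hs CRP, dialyzer type". It does not say whether baseline or updated values are meant.

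On whether the membrane could change the markers, the background before section 2 says of MCO membranes that "positive results have been obtained in some efficacy studies, aimed at evaluating inflammation, and the clearance of medium molecules". Section 3.1.2.1 plans analyses of albumin, PEW, MIS and hs CRP "to assess differences between variables with repeated measures, over time". In section 3.2.1, the table holding PEW and the malnutrition-inflammation scale is footnoted as measured every 6 months.

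The causal diagram and G methods in analysis item 4 are planned with albumin as the exposure, not for the dialyzer contrast.

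**The concern.** IPTW on baseline covariates aims at the total effect of dialyzer type. A marker measured after dialysis has started on a given membrane can be a consequence of that membrane. Holding it constant in the outcome model removes whatever part of the effect runs through it. What is left is at best a direct effect. Even that is biased if an unmeasured factor, such as severity of illness, drives both marker and outcome. The weights cannot help, because they balance the groups only at baseline.

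Mortality, 4-year survival and hospitalization are primary outcomes (section 2.4), and objectives 2 and 4 ask for between-dialyzer comparisons. The weighted Cox HR is the confounding-adjusted estimate described for the time-to-event part. A reader would take it as the effect of the dialyzer, and no text labels it otherwise.

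**Working it through.** **1. What is fixed and what is open**

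| Model | Marker inclusion | Timing |
|---|---|---|
| Cox (item 1) | committed | time-dependent |
| Poisson/negative binomial (item 2) | candidates | not stated |
| Weighted GLM (IPTW step 5) | none named | – |
| Kaplan-Meier and log-rank-type tests (item 1) | none named | – |

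No Cox model without the time-updated markers is named.

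**2. The SAP's own figure.** The sample-size section gives 90% power at an IRR of 0.82 for all-cause hospitalization, with 564 and 534 patients and a significance level of 0.05. Event rate, dispersion and sidedness are not given, so the 90% can be neither reproduced nor refuted. As a guide, with p = 564/1098, Schoenfeld's formula for two-sided 0.05 gives (1.960 + 1.282)² / [p(1 − p)(ln 0.82)²], about 1069 events, or 1069/1098 = 0.97 per patient. The present point does not depend on this. Below, 0.82 is only a yardstick: |ln 0.82| = 0.198.

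**3. Illustration for the albumin pathway.** Both inputs are assumptions that the SAP does not supply: MCO lowers albumin by d = 0.05–0.20 g/dL, and the HR per +1 g/dL is h = 0.4–0.6. Pathway HR = exp(−d × ln h).

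- d = 0.05, h = 0.6: exp(0.0255) = 1.026; 0.0255/0.198 = 13% of the yardstick
- d = 0.10, h = 0.4: exp(0.0916) = 1.096; 46%
- d = 0.20, h = 0.4: exp(0.1833) = 1.201; 92%

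In the last case a total HR of 1.00 would be reported as 1/1.201 = 0.83.

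**4. Simulation check.** Poisson counts for 564 and 534 patients without baseline confounding, eight 6-month intervals, 40 replicates per scenario, total IRR set to 0.82. With A = 1 for MCO and s the assumed share of the log effect that is mediated:

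- marker: M = 0.6·M₀ + a·A + 0.5·U + 0.5·e, with a = s × ln 0.82 / 0.4
- rate per interval: 0.3 × exp[(1 − s)·ln 0.82·A + 0.4·M + b·U]

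M₀ is the baseline marker, e is random noise, and U is an unmeasured factor with outcome effect b.

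| s | No marker, or baseline only | Time-updated marker, b = 0 | Time-updated marker, b = 0.3 |
|---|---|---|---|
| 0% | 0.82–0.83 | 0.82 | 0.83 |
| 25% | 0.82–0.83 | 0.87 | 0.89 |
| 50% | 0.81–0.83 | 0.91 | 0.94 |
| 75% | 0.81–0.83 | 0.94 | 1.01 |
| 100% | 0.81–0.82 | 1.01 | 1.09 |

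Without the marker, or with its baseline value only, the estimate stays near the total effect in every row. With the time-updated marker it moves toward the direct effect 0.82^(1 − s), and beyond it when U also affects the outcome. With nothing mediated it does not move. The simulation uses rate ratios; it shows the mechanism and does not forecast the Cox result.

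**The case against.** The case for the plan has real substance.

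- **Count models.** A reader might infer that these also adjust for post-baseline markers. The SAP does not say so: the markers are candidates and their timing is not given. Baseline values, or no inclusion, fit the text equally well. This stands.
- **Mediation.** A reader might infer that the SAP itself places all four markers on the pathway. The background supports a link to inflammation only. Nothing states that MCO changes albumin, PEW or MIS, and planning to compare markers over time does not assert a difference. This stands, so the markers may lie on the path; the SAP does not establish that they do.
- **Size.** The 92% rests on unanchored albumin assumptions. It scales a hazard ratio for an unspecified outcome against a rate ratio for hospitalization. It is an illustrative upper end, not an expected bias.
- **Other analyses.** Incidence rates, Kaplan-Meier curves and log-rank-type tests do not condition on the markers, so a total difference would not be wholly hidden. But weighting is stated for the Cox models and not for these, and they give no HR. IPTW step 5 is generic, while item 1 specifies the model for these objectives.
- **Study question.** The general objective concerns the markers themselves. Analysis item 4 serves that objective separately, so it does not justify putting the markers in the dialyzer model.

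**Conclusion.** The point holds for the Cox models. As written, the HR for time to death and time to hospitalization equals the total dialyzer effect only if the membrane changes none of the four markers, and the analysis should not depend on that. For the count models the defect is an open choice that allows the same error.

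The documents give no mediated share, so they do not fix the size. Under the stated assumptions the albumin pathway is an HR of about 1.03–1.20. In the simulation a total IRR of 0.82 became about 0.87 to 1.01 as the mediated share rose from 25% to 100%, and up to 1.09 with a shared unmeasured cause. At zero mediation it stayed at 0.82–0.83. The documents do not support the stronger conclusion that the dialyzer estimates are certainly biased, or that harm would be concealed.

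**What to change.** - **Main model.** For the dialyzer comparisons, name one: an IPTW-weighted Cox model (Poisson or negative binomial for counts) with dialyzer as the only regressor, and with baseline albumin, PEW, MIS and hs CRP named in the propensity score. A version that also adjusts for the baseline values is secondary.
- **Markers.** Remove post-baseline markers from these models, and state that any marker entering the count models is the baseline value.
- **Time-updated models.** Keep them only as separately labelled mediation analyses or as albumin analyses under objective 6.
- **Dialyzer change.** Item 1 treats dialyzer type as time-dependent, while the end-of-follow-up table in section 3.2.1 lists a dialyzer change as a reason for ending follow-up. These must be reconciled. If follow-up is censored at a change, baseline weights alone may leave informative censoring. Time-updated markers can then be used in censoring weights instead of as outcome-model covariates.

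The cost is SAP wording and a little more analysis work, mainly if censoring weights are needed. The markers used are already among the planned study variables.

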3.1. General information

3.1.1. Descriptive component:

This study includes demographic variables, medical history, hemodialysis treatment, laboratory parameters, medication, nutritional variables, variables related to hospitalization, variables related to mortality, and end-of-follow-up variables. The descriptive component will be carried out taking into account the continuous, ordinal, or nominal nature of the above variables, taking into account the following procedures:

 Continuous variables: Means or medians will be used as numerical methods to describe variables, along with their corresponding dispersion measures: standard deviation (SD) or interquartile range (IQR). Box plots will be used as graphical methods to evaluate the shape of the distribution, as well as to assess the

- presence of symmetry and extreme values. Normal quantile graphs will be used as a tool to assess the normality of the variables.
- Ordinal variables: Medians (IQR) or absolute and relative frequency measures will be used as summary measures in the case of variables with six or fewer modalities.
 Bar graphs will be used as summary graphic methods.
- 3. Nominal and count variables: Absolute frequencies and percentages will be used for their description using numerical methods. The summary graphic component will be carried out using bar graphs.

For the outcome variables (time between cohort entry and death, time between cohort entry and hospitalization, presence of non-fatal cardiovascular events, and days of hospitalization) their estimators will be calculated together with their 95% confidence intervals.

Each of these analyses will be performed for the entire sample, as well as for each of the exposure groups (MCO and HD AF).

3.1.2. Analytical component:

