3.1.5. Handling missing data

Considering that in the present study data from a standardized clinical registry of proven quality in previous research will be used, a low amount of missing data is expected in the study variables. However, it is noted that the amount or pattern of missing data may affect the quality of the statistical estimates. Missing data and the mechanism by which they occur will be evaluated: MCAR (Missing Data). completely at random), MAR (Missing at random) and MNAR (Missing not at random), according to this evaluation, the appropriate data imputation procedures will be defined for each case

3.1.5 . Sample size:

Based on the availability of the assembled cohorts of 1098 patients, 564 on MCO in the Theranova® dialyzer cohort and 534 on conventional HD in the AF dialyzer cohort. This provides 90% power considering an IRR 0.82 for all-cause hospitalization and a significance level of 0.05 (26).

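### The first primary outcome, hospitalization events per patient-year, carries the IRR-based power statement but is not assigned to the count models; its named between-cohort comparison is time to event

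*SAP*

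**What the plan says.** - SAP 2.4 lists as the first primary outcome "Incidence of hospitalization events (per patient-year". Objective 2 in SAP 2.2 is "To estimate and compare the days of hospital stay and the incidence of mortality and hospitalization in the studied cohorts".
- SAP 3.1.5, Sample size, gives the cohorts as "564 on MCO in the Theranova® dialyzer cohort and 534 on conventional HD in the AF dialyzer cohort" and adds: "This provides 90% power considering an IRR 0.82 for all-cause hospitalization and a significance level of 0.05". No other outcome has a power statement.
- SAP 3.1.2.2, analysis item 1, covers hospitalization and death together. It begins: "For the objectives related to the comparison of time to hospitalization and time to death event between both cohorts, the respective incidence rates for each". Its methods are incidence rates by cohort, Kaplan-Meier curves, a choice of rank tests, and IPTW-weighted Cox models that report HRs.
- SAP 3.1.2.2, analysis item 2, begins: "To meet the objectives related to counting variables (days of hospitalization and non-fatal cardiovascular events), Poisson regression models or negative binomial". Candidate covariates are then listed for hospital days and for non-fatal cardiovascular events only.
- SAP 3.1.1 lists the hospitalization outcome variable as "time between cohort entry and hospitalization", and lists no number of admissions.
- Step 5 of the propensity-score procedure in 3.1.2.2 says in general terms that treatment effects come from weighted generalized linear models chosen by kind of outcome.

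**The concern.** Events per patient-year is a recurrent-event rate, and the effect measure that matches it is the rate ratio used in the sample-size statement. The plan goes outcome by outcome, gives rate models to one other primary outcome and to the secondary outcome, and leaves this one with a hazard ratio for time to hospitalization.

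The two measures answer different questions. A Kaplan-Meier or ordinary Cox analysis of one entry-to-hospitalization time takes one admission per patient, so later admissions do not contribute. If patients differ in their underlying admission rate, the first-event HR also lies closer to 1 than the rate ratio. The stated 90% would then belong to an analysis that the plan does not clearly contain. In a non-randomized comparison, unweighted group incidence rates cannot stand in for the adjusted estimate.

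**Working it through.** **Inputs from the SAP.** 564 and 534 patients (total 1,098, MCO share 564/1098 = 0.5137), ratio 0.82, alpha 0.05, power 90%. Sidedness is not stated; two-sided is assumed.

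**The stated 90%.** It cannot be reproduced, because the SAP gives no baseline rate, follow-up per patient or dispersion. It can be inverted to show what it requires. For a Wald test on the log rate ratio, with m0 and m1 = 0.82·m0 the mean admissions per patient and k the negative binomial dispersion:

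var = (1/m1 + k)/564 + (1/m0 + k)/534

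90% power needs var = (ln 0.82)² / (1.960 + 1.282)² = 0.03938/10.507 = 0.003748.

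- k = 0 (Poisson): m0 = 1.08 admissions per high-flux patient, about 1,073 in total.
- k = 0.5: m0 = 2.10.
- k = 1: m0 = about 39.
- k above about 1.03: not reachable, since k·(1/564 + 1/534) alone exceeds 0.003748.

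So a rate analysis can meet the stated 90% if dispersion is moderate.

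**What the time-to-event comparison needs.** By Schoenfeld:

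D = (1.960 + 1.282)² / [0.5137 × 0.4863 × (ln 0.82)²] = 10.507 / (0.24981 × 0.03938) ≈ 1,068 events

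Freedman's formula gives 1,075. With one event per patient the maximum is 1,098, and 1,068/1,098 = 97%. If every patient were admitted, power at HR 0.82 would be Φ(√(1098 × 0.24981) × 0.1985 − 1.960) = Φ(1.33), about 91%. With a one-sided test the requirement is 871 events, or 79% of patients.

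**Illustrative comparison.** Rates, follow-up and k here are assumptions, not SAP figures. With constant rates, gamma heterogeneity of variance k and full follow-up t, the share admitted is p = 1 − (1 + k·m)^(−1/k), and the marginal hazard is r/(1 + k·r·t). First-event power uses Schoenfeld at the event-weighted average HR; count-model power uses the variance above.

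Worked case, 0.9 per year, 2 years, k = 0.5: m0 = 1.8 and m1 = 1.476, so p0 = 1 − 1.9⁻² = 0.72 and p1 = 1 − 1.738⁻² = 0.67. First events ≈ 763 of 534 × 1.8 + 564 × 1.476 ≈ 1,794 admissions (43%). The average HR is 0.854.

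| High-flux rate/yr, years, k | First events | Share of all admissions | First-event HR | Power, first event | Power, count model |
|---|---|---|---|---|---|
| 0.5, 2, ≈0 | 653 | 66% | 0.82 | 71.7% | 87.8% |
| 0.5, 2, 0.5 | 577 | 58% | 0.844 | 53.0% | 73.7% |
| 0.9, 2, ≈0 | 881 | 49% | 0.82 | 83.7% | 98.7% |
| 0.9, 2, 0.5 | 763 | 43% | 0.854 | 58.9% | 87.6% |
| 0.9, 2, 1 | 679 | 38% | 0.872 | 43.0% | 73.4% |
| 1.2, 4, ≈0 | 1,082 | 23% | 0.82 | 90.3% | about 100% |
| 1.2, 4, 0.5 | 988 | 21% | 0.867 | 60.8% | 97.0% |

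Across the whole grid (0.5 to 1.2 per year, 1 to 4 years, k from 0 to 1.5), first admissions were 17% to 80% of all admissions. The first-event HR was about 0.84 to 0.90 for k of 0.5 to 1.5. The count model had more power throughout.

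Simulated cohorts with a 4-year limit and loss at 0.25 per year agreed in direction. First event against rate ratio gave 53% against 86% at 0.8 per year, k = 0.5, and about 64% against 92% at 1.2 per year, k = 0.5.

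**The case against.** **Step 5 can be read to cover this.** Weighted generalized linear models chosen by kind of outcome could include a count model for admissions. That is fair, and it rules out the inference that the plan decides against a weighted IRR. But the outcome-specific list that follows names the count outcomes and omits this one, so at best the method for a primary outcome is left open.

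**The SAP never says first hospitalization, and it calculates incidence rates by group.** Both are true. A reader might infer that repeat admissions are deliberately discarded; the text does not say so. One admission per patient is inferred from a single entry-to-hospitalization time, Kaplan-Meier and Cox models, and the absence of any recurrent-event method. Repeat admissions may enter the group rates, but those are not an adjusted comparison.

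**Item 4 models hospitalization events.** It does, with mixed models and G methods, but for the association with albumin. It does not supply the between-cohort IRR.

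**The power losses depend on assumptions.** This stands. With no dispersion there is no attenuation of the HR and the gap narrows. For k above about 1.03 the rate analysis itself cannot reach the stated 90%, so such scenarios conflict with the SAP's own figure. The calculations also ignore the variance added by IPTW and death as a terminal event. No single power figure should be taken as the study's actual power.

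**Conclusion.** The mismatch holds. The outcome is a rate and the power statement is for a rate ratio, but the named between-cohort comparison is a hazard ratio for time to hospitalization, and no sentence assigns a weighted IRR to this outcome.

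The firm part of the size rests on SAP figures plus a two-sided test and one event per patient: about 1,068 of 1,098 patients (97%) would need an admission for the time-to-event comparison to have 90% power at 0.82. The further power loss and the drift of the HR toward 1 are illustrative. The advantage of the rate analysis appeared in every scenario, but its amount is not fixed by the document.

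Two stronger conclusions are tempting and not supported. The plan does not exclude a weighted IRR, given step 5. Nor is the stated 90% shown to be wrong, because the inputs needed to check it are not given.

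**What to change.** In SAP 3.1.2.2, item 2, add hospitalization events to the count outcomes: an IPTW-weighted model of all-cause admissions (negative binomial, or Poisson with robust variance), with log person-time at risk as offset, reporting the between-cohort IRR with 95% CI. State that this is the comparison matching the sample-size statement. Keep the Kaplan-Meier, rank-test and Cox analyses as supportive, and label them time to first hospitalization if that is what is meant.

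The cost is a line or two of SAP text. The analysts should also confirm that the data extract holds the number of admissions and the follow-up time per patient, since Table 7 shows only hospitalization yes or no and days of stay. The primary outcome already requires both quantities. The change should be made before the outcome data are analysed.
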